**End of study Date (for interim analysis only)**

For subjects who completed the study or early terminated from the study as of the data cut-off date, the end of study date is the date on the end of study form. For subjects who are ongoing as of cutoff date, leave the end of study date as missing.

**End of study Date (for final analysis only)**

Use the end of study date from the End of Study Form.

**Study Visit**

Since the actual visit for a subject may not exactly coincide with their scheduled visit date, the actual visit date is mapped to the study visit as follows.

Analysis window for ionized calcium and cinacalcet dose:

Analysis Visit	Target Day	Study Day	Interval (days)
Baseline (for ionized calcium)	1	<= 1	N/A
Day 1 (for cinacalcet dose)	1	1	1
Week 1	8	2 – 11	9
Week 2	15	12 – 18	7
Week 3	22	19 – 25	7
Week 4	29	26 – 32	7
Week 5	36	33 – 39	7
Week 6	43	40 – 46	7
Week 7	50	47 – 53	7
Week 8	57	54 – 60	7
Week 9	64	61 – 67	7
Week 10	71	68 – 74	7
Week 11	78	75 – 81	7
Week 12	85	82 – 88	7
Week 13	92	89 – 95	7

Page 1 of 2

Product: Cinacalcet HCl  
Statistical Analysis Plan: 20140159  
Date: 24 May 2016

Page 11 of 36

**Analysis window for ionized calcium and cinacalcet dose:**

Analysis Visit	Target Day	Study Day	Interval (days)
Week 14	99	96 – 102	7
Week 15	106	103 – 109	7
Week 16	113	110 - 116	7
Week 17	120	117 – 123	7
Week 18	127	124 – 130	7
Week 19	134	131 – 138	7
Week 20	141	139 – 144	7
Week 21	148	145 – 152	7
Week 22	155	153 – 158	7
Week 23	162	159 – 166	7
Week 24	169	167 – 173	7
Week 25	176	174 – 180	7
Week 26	183	181 – 187	7
Week 27	190	188 – 194	7
Week 28	197	≥195	N/A

Page 2 of 2

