# AMGEN'

Page 43 of 79

Page 45
---------

Product	Cinacalcet HCI										
Protoco	I Number:	20140159									
Date: 0	1 June 201	6									

Page 44 of 79

Note: When it is not possible to perform a study visit at the specified time point, the visit may be performed within ± 3 days.

1 - Where the Screening and day 1 assessments for Study 20140159 overlap with visits in the Studies 20130356 or 20110100, these will be performed once at the site and applied to both study visits to minimize duplicate study assessments.

2 - These procedures are required for Study 20140159 screening visit if > 14 days since last study visit in Studies 20130356 or 20110100 for subjects impacted by study termination. 3 - Biomarker Assessments and 25 (OH) Vit D are not required for subjects previously enrolled in 20110100. If baseline FGF23 is not collected at day 1, it must not be collected at week 28.

Refer to the applicable supplemental laboratory manuals for detailed collection and handling procedures.

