#### 7.2 General Study Procedures

All on-study visits and dosing should be scheduled from day 1. Week 1 begins one week after the day 1 visit. It is important to perform study assessments and obtain samples at the time points outlined in the Schedule of Assessments in Section 7.1.

The duplicate study assessments will be collected once for both studies as described in Section 7.2.2.

When it is not possible to perform a study visit at the specified time point, the visit may be performed within  $\pm$  3 days. If a study visit is missed, subsequent visits should resume on the original visit schedule. Missed assessments at prior visits should not be duplicated at subsequent visits.

With the exception of screening assessments, all study procedures for a visit must be completed on the same day.

It is the responsibility of the investigator to ensure that all procedures are performed according to the protocol.

Any blood or serum collected according to the Schedule of Assessments may be analyzed for any of the tests outlined in the protocol and for any tests necessary to ensure subject safety. This includes testing to ensure analytical methods produce reliable and valid data throughout the course of the study. This may also include, but is not limited to, investigation of unexpected results, incurred sample reanalysis, and analyses for method transfer and comparability.

Details regarding each type of procedure are provided in Section 7.3

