**AMGEN** 

# 7.2.3 Treatment

The following procedures will be completed during the 28-week treatment period at the times designated in the Schedule of Assessments (Table 4). Study visits will occur weekly  $\pm$  3 days. All blood samples for laboratory assessments for hemodialysis subjects are to be collected prior to initiating the dialysis session during the visit. Cinacalcet will be dispensed to subjects to take home for daily administration at the conclusion of the study visit weekly.

The following procedures and assessments will be completed at the times designated in the Schedule of Assessment (Table 4, Section 7.1) and recorded on the eCRF:

- concomitant medications
- documentation of subject compliance with daily administration of cinacalcet
  - o patient diary review
  - o counts of returned bottles of tablets/capsules/suspension
- adverse events, including signs and symptoms of hypocalcemia, seizures, and infections
- serious adverse events
- ionized calcium
- central laboratory assessments including the following:
  - o serum calcium, serum albumin, and calculation of cCa, phosphorous
  - o iPTH
  - LFT (weeks 11 & 23)

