**Study day**

For a given study visit, the study day is defined as: study day = (visit date - date of Study Day 1) +1.

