**Analysis window for vital signs and all other labs.**

Study Visit	Target Day	Study Day	Interval (days)
Baseline	1	≤ 1	N/A
Week 3	22	2-36	35
Week 7	50	37-64	28
Week 11	78	65-92	28
Week 15	106	93-120	28
Week 19	134	121-148	28
Week 23	162	149-176	28
Week 27	190	177 – 194	18
Week 28	197	195 – 211	17
Week 32	225	≥212	N/A

If there is more than one observation in a visit window, use the value collected closest to the target day. If multiple observations are equally close to the target day, use the later value.

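### A one-day slip in the SAP visit windows gives the previous week's label to ionized calcium visits held exactly 3 days early at Weeks 20, 22 and 24 to 28, and to Week 28 vital signs and other laboratory tests taken on day 194.

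*SAP*

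**What the plan says.** Protocol 7.2 counts visits from day 1: "Week 1 begins one week after the day 1 visit". SAP 6.2 defines "study day = (visit date - date of Study Day 1) +1". The note under Table 4 in protocol 7.1 gives the tolerance: "When it is not possible to perform a study visit at the specified time point, the visit may be performed within ± 3 days". Protocol 7.2 and 7.2.3 repeat it.

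SAP 6.2 maps actual visit dates to analysis visits through four window tables. In the table for ionized calcium and cinacalcet dose, Weeks 2 to 18 are target ±3 days; the last such row is "Week 18 127 124 – 130 7". Two rows later the table reads "Week 20 141 139 – 144 7" (week, target day, study-day range, interval in days). The table for vital signs and all other labs contains "Week 28 197 195 – 211 17", preceded by a Week 27 window of days 177 to 194. A rule printed once, after the last table, deals with duplicates: "If there is more than one observation in a visit window, use the value collected closest to the target day". Ties go to the later value.

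SAP 10.7.2 summarizes ionized calcium, most chemistry, hemoglobin, bone biomarkers, FGF23, 25(OH)D and testosterone at scheduled visits. SAP 10.7.3 does the same for vital signs.

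**The concern.** A window table should give every protocol-compliant visit its own week. From Week 19 the ionized calcium table stops doing so, and the printed interval column no longer matches the printed bounds. An affected visit is 3 days from its own target and 4 days from the target of the week it is assigned to, so a deliberate nearest-target allocation does not explain it.

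At stake are by-visit safety and biomarker rows. Ionized calcium is drawn weekly and is a named risk-mitigation measure (protocol 2.4). The affected weeks include monthly visits 20 and 24 and the end-of-treatment visit. Bone biomarkers, FGF23 and male testosterone are scheduled only on day 1 and at Week 28 (protocol Table 4). A child whose Week 28 sample is labelled Week 27 therefore contributes no change from baseline at the visit where that change is reported.

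**Working it through.** **Inputs.** Target day, bounds and printed interval come from SAP 6.2; the ±3-day tolerance comes from the protocol.

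**Formulas.** Target day = 7 × week + 1. Window length = last day − first day + 1. For each scheduled week, every day from target − 3 to target + 3 is assigned to its printed window and the label compared with the true week.

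**What reproduces.** All printed target days do (Week 20: 7 × 20 + 1 = 141; Week 28: 7 × 28 + 1 = 197). In the ionized calcium table the printed length of 7 reproduces for Weeks 2 to 18 (Week 18: 130 − 124 + 1 = 7) and Weeks 24 to 27. It does not for Weeks 19 to 23 (Week 20: 144 − 139 + 1 = 6).

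| Week | Target | Printed days | Printed length | Actual length | Offset from target | Day of visit 3 days early | Label given |
|---|---|---|---|---|---|---|---|
| 19 | 134 | 131–138 | 7 | 8 | −3 to +4 | 131 | 19 |
| 20 | 141 | 139–144 | 7 | 6 | −2 to +3 | 138 | **19** |
| 21 | 148 | 145–152 | 7 | 8 | −3 to +4 | 145 | 21 |
| 22 | 155 | 153–158 | 7 | 6 | −2 to +3 | 152 | **21** |
| 23 | 162 | 159–166 | 7 | 8 | −3 to +4 | 159 | 23 |
| 24 | 169 | 167–173 | 7 | 7 | −2 to +4 | 166 | **23** |
| 25 | 176 | 174–180 | 7 | 7 | −2 to +4 | 173 | **24** |
| 26 | 183 | 181–187 | 7 | 7 | −2 to +4 | 180 | **25** |
| 27 | 190 | 188–194 | 7 | 7 | −2 to +4 | 187 | **26** |
| 28 | 197 | ≥195 | N/A | open | from −2 | 194 | **27** |

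No other day within tolerance is mislabelled. Weeks 19, 21 and 23 keep all their own days.

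**What happens to the value.** Take a Week 19 visit on day 134 and a Week 20 visit on day 138. Both fall in 131–138. Day 134 is 0 days from target and day 138 is 4, so the Week 20 value is discarded and Week 20 is empty. For Week 28 on day 194: if the Week 27 visit was on days 188 to 193 it is at most 3 days from 190 and is kept, and the day-194 value is dropped. If the Week 27 visit was on day 187 it is itself labelled Week 26, and the day-194 value becomes Week 27. In both cases Week 28 has no value from the Week 28 visit.

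**Vital signs and all other labs.** One day within tolerance is mislabelled: day 194 goes to Week 27 (177–194). Vital signs on day 194 lose to any Week 27 reading on days 187 to 193. Chemistry, hematology, 25(OH)D, biomarkers, FGF23 and testosterone have no Week 27 draw, so the sample stands under a week at which the test is not scheduled.

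**Other tables.** The iPTH table and the calcium and phosphorus table mislabel no visit within tolerance; their Week 28 window is 177–211.

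**Other interval misprints.** Ionized calcium Week 1 (2–11) is 10 days, printed 9. Week 3 in the calcium and phosphorus table (15–36) is 22 days, printed 21. Neither mislabels a visit.

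**Size.** The documents give no distribution of visit days, so the share at −3 days is assumed.
- 5%: 0.05 × 78 = 3.9 and 0.05 × 48 = 2.4.
- Even spread over seven days, 1/7 or 14%: 78/7 = 11.1 and 48/7 = 6.9.

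The 78 is the planned enrolment. The 48 is the planned size of Study 20130356, the only source of subjects for the bone biomarkers and FGF23.

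**The case against.** The best case against this is that it is a small slip in rows that decide nothing. Much of that stands.

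- A reader might infer that Week 28 values drop out generally, or that both tables are shifted late in treatment. The documents do not support this. Days 195 to 200 map correctly to Week 28, only visits exactly 3 days early fail, and the vital signs and other labs table has one wrong boundary.
- A reader might infer that the Week 23 and 28 efficacy results are compromised. They are not: iPTH, corrected calcium and phosphorus use other, sound windows.
- A reader might infer that low-calcium signals are lost. The primary endpoint is subject incidence of events of interest, which uses no visit window. The incidence of ionized calcium below 1.05, 1.00 and 0.94 mmol/L at any time, and the worst-grade shifts, still count a relabelled value.
- Dose shares the ionized calcium table, but dose level is recorded daily (SAP 6.5 and 9.3.1), so a record on or near the target day is normally available. SAP 10.7.5 lists no by-visit dose table. The effect on dose is slight.
- Chemistry, hematology and 25(OH)D are drawn again at Week 32, so those children keep a post-baseline result. Subjects who stop early have their end-of-treatment tests at early termination (protocol 7.2.5).
- The protocol allows the tolerance only when the scheduled day is not possible, so an even spread over seven days may be too high. Attrition and the entry criteria for the standard-of-care arm also reduce 78 and 48.

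The objection does not remove the error. The interval column contradicts the bounds, the rows are contiguous, and the 194/195 boundary appears in two tables, so a PDF reading fault is unlikely.

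**Conclusion.** The bounds are wrong as written, within a narrow scope. Seven of the 28 weekly ionized calcium windows, and the Week 28 window for vital signs and other labs, fail for a compliant visit exactly 3 days early. The consequence is mislabelled or discarded values in descriptive by-visit summaries. The most costly case is a bone biomarker, FGF23 or testosterone sample on day 194, because it is the only scheduled post-baseline draw.

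Assuming that 5% to 14% of visits fall 3 days early, about 4 to 11 of 78 children are affected at Week 28, or 2 to 7 of 48 for the biomarkers. For these shares the counts are upper limits, because they take full planned enrolment with no attrition. The number of boys with testosterone results is not given, so no count is offered for that test. The correction should be made, but no conclusion on the primary or secondary endpoints depends on it.

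**What to change.** In the ionized calcium and cinacalcet dose table, set the windows to target ±3 days:

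- Week 19: 131–137
- Week 20: 138–144
- Week 21: 145–151
- Week 22: 152–158
- Week 23: 159–165
- Week 24: 166–172
- Week 25: 173–179
- Week 26: 180–186
- Week 27: 187–193
- Week 28: ≥194

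Split the vital signs and all other labs table in two. For vital signs, use Week 27 = 177–193 (17 days) and Week 28 = 194–211 (18 days). For laboratory tests not drawn at Week 27, delete the Week 27 row and use Week 28 = 177–211, as the iPTH table already does. With these bounds no visit within tolerance is mislabelled. Correct the two other printed interval lengths (10 and 22 days) at the same time.

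The cost is a SAP table edit and a change of programming parameters before database lock. No new data are needed.

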**Analysis window for iPTH**

Study Visit	Target Day	Study Day	Interval (days)
Baseline	1	<= 1	N/A
Week 3	22	2-36	35
Week 7	50	37-64	28
Week 11	78	65-92	28
Week 15	106	93-120	28
Week 19	134	121-148	28
Week 23	162	149-176	28
Week 28	197	177-211	35
Week 32	225	≥212	N/A

**Analysis window for calcium, corrected total serum calcium, serum phosphorus, serum albumin, CaxP**

Study Visit	Target Day	Study Day	Interval (days)
Baseline	1	<= 1	N/A
Week 1	8	2-14	13
Week 3	22	15-36	21
Week 7	50	37-64	28
Week 11	78	65-92	28
Week 15	106	93-120	28

Page 1 of 2

**AMGEN®**

**AMGEN®**

Product: Cinacalcet HCl  
Statistical Analysis Plan: 20140159  
Date: 24 May 2016

Page 12 of 36

**Analysis window for calcium, corrected total serum calcium, serum phosphorus, serum albumin, CaxP**

Study Visit	Target Day	Study Day	Interval (days)
Week 19	134	121-148	28
Week 23	162	149-176	28
Week 28	197	177-211	35
Week 32	225	≥212	N/A

Page 2 of 2

**Analysis window for vital signs and all other labs.**

Study Visit	Target Day	Study Day	Interval (days)
Baseline	1	≤ 1	N/A
Week 3	22	2-36	35
Week 7	50	37-64	28
Week 11	78	65-92	28
Week 15	106	93-120	28
Week 19	134	121-148	28
Week 23	162	149-176	28
Week 27	190	177 – 194	18
Week 28	197	195 – 211	17
Week 32	225	≥212	N/A

If there is more than one observation in a visit window, use the value collected closest to the target day. If multiple observations are equally close to the target day, use the later value.

### 6.3 Demographics and Baseline Characteristics

#### Demographics

Sex, ethnicity, race, age at enrollment of parent studies will be transferred from the parent studies 20130356 and 20110100. Study baseline age at Study Day 1 of Study 20140159 is defined as the subject's age (in years) on the day of enrollment in study 20140159.

#### StudyBaseline Values

##### StudyBaselineatStudyDay1ofStudy20140159

Study Baseline iPTH, corrected total serum calcium, and serum phosphorus values are defined as the mean values of samples collected during the screening period and Study Day 1 pre-dose.

---

Product: Cinacalcet HCl  
Statistical Analysis Plan: 20140159  
Date: 24 May 2016

Page 13 of 36

---

Ca x P will be calculated at central lab COVANCE using corrected total serum calcium and serum phosphorus. **Study** Baseline value will be the mean of the values during the screening period and **Study** Day 1 pre-dose.

Study Baseline dry weight is defined as the value collected at **Study 20140159** Day 1 visit.

For all other variables, the **study** baseline value is defined as the last non-missing value collected prior to the first dose of IP, either during the screening phase or on Study Day 1.

All **study** baseline values will be calculated to the same number of decimal places as the raw data.

**Study**Baseline vitamin D use

Vitamin D use at **study** baseline is defined as any use of nutritional vitamin D or vitamin D sterol within 7 days prior to Study Day 1.

**Study**Baseline growth hormone use

Growth hormone use at **study** baseline is defined as any use of growth hormone during the screening period prior to Study Day 1.

**Study**Baseline phosphate binder use

Phosphate binder use at **study** baseline is defined as any use of any phosphate binder the day prior to Study Day 1.

**Study**Baseline calcium supplement use

Calcium supplement use at **study** baseline is defined as any use of any calcium supplement the day prior to Study Day 1.

**Baseline at first cinacalcet dose (combined studies 20130356, 20110100 and 20140159)**

**For subjects who received SOC only in Study 20130356, baseline values at first cinacalcet dose are same as study baseline at Study Day 1 of Study 20140159.**

**For other subjects, all baseline values at first cinacalcet dose will be transferred from the parent studies 20130356 and 20110100.**

#### 6.4 Study Endpoints

##### Treatment emergent adverse events

###### **20140159studyonly**

Treatment-emergent adverse events are defined as adverse events that occurred on or after Study Day 1 in **Study 20140159**.

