#### **Investigational Product**

**Amgen Investigational Product Dosage and Administration:** Cinacalcet is a calcimimetic agent which is synthesized as a hydrochloride salt. Cinacalcet will be provided as 5 mg capsules for sprinkling or as film coated tablets for swallowing in a strength of 30 mg.

The capsules provided must not be swallowed whole and must be opened and either sprinkled on soft food or suspended into a sucrose syrup to create a liquid suspension for administration.

The protocol-specified doses (PSD) for use in this study are: 1, 2.5, 5, 7.5, 10, 15, 30, 60, 90, 120, and 180 mg.

Subjects will receive cinacalcet daily and all doses should be administered with food or shortly after a meal at the same time each day. On study visit days where a blood sample is to be drawn, cinacalcet should not be administered until after the blood sample has been obtained.

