## 7.3.10 Adverse Events

Adverse events will be collected in the eCRF for each subject at all study visits. Targeted questions regarding hypocalcemia, seizures and infections will be asked and data will be entered into the eCRF at each study visit.

All clinically significant (according to the investigator's judgment), laboratory abnormalities will be reported as adverse events. In assessing clinical significance of a low serum calcium value, the investigator should consider factors such as presence of clinical symptoms associated with hypocalcaemia, dose adjustment of cinacalcet or concomitant medications (eg, vitamin D, phosphate binders). In addition, the investigator should indicate on the eCRF whether hypocalcemia was symptomatic, and if so provide the accompanying symptoms.

Serious adverse events that occur in a subject from the date of the first dose through 30 days after the last dose of IP will be recorded in the adverse event eCRF. All adverse events that occur from the date of the first dose through 30 days after the last dose of IP will be recorded in the adverse event eCRF. Refer to Section 9 for additional information.

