**Study Day 1**

The date that the initial dose of IP is administered in Study 20140159. For subjects who didn't take any IP throughout the study, leave as missing.

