###### **Combined20130356,20110100&20140159Studies**

Treatment-emergent adverse events are defined as adverse events that occurred on or after day 1 of cinacalcet treatment in the parent study (Studies 20140356 and 20110100) or Study 20140159.

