**9.3.2 Handling of Missing Data**

**9.3.2.1 Missing Adverse Event date**

**For any listings, missing or incomplete dates will be listed as is.**

All missing dates (missing entirely or partially) of adverse events occurring after first dose of IP will be queried. **For adverse events with the question “Did event start before first dose of investigational product?” on the eCRF was answered as “Yes”, the missing adverse event start dates won’t be imputed.** All other missing adverse event start dates will be handled as described below:

**When the adverse event start year is available and the start day and month are missing, if the start year is the same as the year of Study Day 1, the start date will be set to date of Study Day 1, otherwise set to the 1st of January of the onset year.**

**When the start year and month are available and the start day is missing, if the start year and month are the same as the year and month of Study Day 1, the start date will be set to date of Study Day 1, otherwise the 1st of the month of the onset year.**

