#### **10.5 Analysis of Primary Endpoint**

The primary endpoint is incidence of treatment emergent adverse events of interest as defined in **Section 6.4**. The analysis will be based on Safety Analysis Set. Subject incidence of EOIs will be summarized by EOI category and **preferred term for data in Study 20140159 only for both the interim and final analyses. The 95% confidence intervals (CI) of the overall subject incidence rates will be reported.**

**The secondary analysis of the primary endpoint is follow-up time adjusted incidence of EOIs for combined data from parent studies and data from the 20140159 study for the final analysis.**

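### SAP 6.4 defines treatment-emergent by calendar date alone, so a new event dated on the first-dose date but recorded as starting before that dose counts in the primary endpoint

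*SAP*

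**What the plan says.** The definition for the extension study (SAP 6.4) is: "Treatment-emergent adverse events are defined as adverse events that occurred on or after Study Day 1" of Study 20140159. SAP 6.2 fixes Study Day 1 as follows: "The date that the initial dose of IP is administered in Study 20140159". The combined-studies definition in SAP 6.4 has the same form: "adverse events that occurred on or after day 1 of cinacalcet treatment in the parent study" or in Study 20140159.

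The extension-study definition feeds the primary analysis. SAP 10.5 states: "The primary endpoint is incidence of treatment emergent adverse events of interest as defined in" SAP 6.4. Protocol 7.3.10 sets the collection window by date as well: "All adverse events that occur from the date of the first dose through 30 days after the last dose of IP". The protocol gives no narrower definition of treatment-emergent.

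The order of events on day 1 is also stated. On visit days with a blood draw, "cinacalcet should not be administered until after the blood sample has been obtained" (Protocol Synopsis, Investigational Product). Protocol 7.2.2 lists ECG, blood pressure, ionized calcium and central laboratory tests among the day 1 procedures, and has IP dispensed after the assessments and enrolment. Under Protocol 7.3.10, clinically significant "laboratory abnormalities will be reported as adverse events".

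The eCRF asks: "Did event start before first dose of investigational product". The SAP mentions this question only in 9.3.2.1, where a yes answer stops imputation of a missing start date.

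**The concern.** The definition cannot tell apart the hours before and after the first dose on the same date, although the trial collects the information that would do so. Two other parts of the SAP do draw that line. Baseline values in SAP 6.3 are taken from samples before the first dose, including those on Study Day 1. SAP 9.3.2.1 declines to place an undated event on Study Day 1 when the site has said it began before dosing.

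One day 1 calcium sample could therefore contribute to the pre-treatment baseline in the laboratory tables and, if reported as a new adverse event, count as treatment-emergent hypocalcemia in the primary endpoint. For a child from the former standard-of-care arm, that event arose before any study cinacalcet. For a pretreated child, it arose before the first extension dose.

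**Working it through.** **1. How the stated rules treat an event.** These cases follow from SAP 6.2, 6.4 and 9.3.2.1:

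- Onset before Study Day 1, flagged as pre-dose: not treatment-emergent.
- Onset on Study Day 1, flagged as pre-dose: treatment-emergent as written. This is the gap.
- Start date missing, flagged as pre-dose: not imputed. The SAP does not state whether it is treatment-emergent.
- Onset on Study Day 1, question answered no: treatment-emergent, as intended.
- Start date wholly missing, question blank: imputed to Study Day 1, so treatment-emergent. A partial date that matches the year, or the year and month, of Study Day 1 is handled the same way.

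The second and third cases can be the same clinical event. Only the completeness of the date differs.

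**2. Who is affected under the combined definition.** For former standard-of-care children, day 1 of cinacalcet treatment is Study Day 1 of the extension, so the same gap applies there. Pretreated children have already passed that day in the parent study, so their extension day 1 is not the boundary. For them the question arises at the parent-study day 1, and these documents do not say whether the parent eCRF holds the flag.

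**3. Size.** SAP 3.2 gives 48 + 30 = 78 planned subjects, which reproduces the stated figure. The endpoint is subject incidence, so a miscounted child changes a category only if that child has no later event in it.

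- Overall, the shift per miscounted child is 1/78 = 1.28 points.
- In one former arm of Study 20130356 it is 1/24 = 4.17 points. This assumes 24 per arm (48 randomized 1:1, Protocol 2.5.1) and that all roll over.

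Illustrative counts (assumed), with Clopper-Pearson 95% intervals:

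| N | Events | Incidence | 95% CI |
|---|---|---|---|
| 78 | 0 | 0.0% | 0 to 4.6% |
| 78 | 1 | 1.3% | 0.0 to 6.9% |
| 78 | 4 | 5.1% | 1.4 to 12.6% |
| 78 | 5 | 6.4% | 2.1 to 14.3% |
| 24 | 0 | 0.0% | 0 to 14.2% |
| 24 | 1 | 4.2% | 0.1 to 21.1% |

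The shift from one child is small against the width of the intervals. The number of children affected cannot be derived, because no day 1 event rate is given.

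**The case against.** The strongest reply is that few events can take this route.

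- Events ongoing from the parent study are entered as concurrent conditions in medical history (Protocol 7.2.2, 7.3.3 and 9.2). The day 1 visit normally doubles as the last parent visit, so a finding there may well be recorded that way.
- Study Day 1 is the dosing date, not the visit date. If the first dose is withheld or taken later, a finding at the visit falls before Study Day 1 and is already excluded.
- The entry and dispensing checks thin out the more marked calcium and QTc findings on a day when dosing goes ahead: exclusion 219 on QTc, inclusion 107 on corrected calcium for the former standard-of-care arm, and the ionized calcium requirement in Protocol 6.2.3.
- Protocol 9.2.1 asks for a clinically significant change from baseline, and the day 1 sample is itself part of baseline.

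All of this stands as a limit on frequency, but none of it repairs the definition. The protocol does not say which record takes a new event first found before dosing at the shared visit, and Protocol 7.3.10 leaves reporting of laboratory abnormalities to the investigator's judgment.

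A reader might infer that every abnormal day 1 sample becomes a treatment-emergent event. The safeguards above show otherwise. A reader might also infer that rare event types suffer most. That does not follow: the route runs mainly through laboratory findings such as hypocalcemia, which Protocol 2.4 names among the most commonly observed events. Fractures, tumors or pancreatitis are not typical findings of a day 1 blood draw.

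**Conclusion.** The gap is real on the text but minor. As written, a new event dated on the first-dose date and recorded as starting before the dose is counted in the primary endpoint. This conflicts with the SAP's own pre-dose baseline rule and with its handling of the same eCRF answer when the date is missing.

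The direction is an overcount of events attributed to the extension treatment period. The size is 1.3 points per miscounted child among 78, or 4.2 points in one former arm under the 24-per-arm assumption. The documents do not support a claim that the primary result would be materially distorted: they give no rate of such events, the analysis is descriptive, and several procedures keep the number low. The change is worth making because it concerns the primary endpoint and the deciding variable is already collected.

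**What to change.** In SAP 6.4, define treatment-emergent as onset on or after Study Day 1, excluding events for which the eCRF pre-dose question is answered yes. State two consequences explicitly:

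- A blank answer still counts as treatment-emergent. Requiring an explicit no would drop day 1 events with an unanswered question, including those that SAP 9.3.2.1 imputes to Study Day 1, and so would undercount harm.
- A flagged event with a missing start date is not treatment-emergent.

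List flagged day 1 events separately. Protocol 9.1.1 records an event that worsens as a single entry at its worst grade, so worsening after dosing could otherwise disappear with the excluded record.

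Apply the same rule to the combined definition for former standard-of-care subjects. Apply it at the parent-study day 1 only where the parent eCRF holds the flag.

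The cost is a short addition to SAP 6.4, one condition in the adverse event derivation and one listing. No new data are needed for the extension study.
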